Hydroxyurea a known substance to interfere with CGM sensor values is started approximately day 7 post-TPIAT and can result in erroneously elevated glucose sensor value 6-9 hours post-administration [2]. For this reason, data from 10 hours post Hydroxyurea dosing will not be used in the initial data analysis.

Study Intervention:

Enrolled participants will NOT have a lead apron used to cover their Dexcom G6 transmitter during radiation exposure procedures performed while participant is inpatient post TPIAT.

Transmitter accuracy and precision will be monitored for 3 months post TPIAT or until the transmitter is changed.

Study Procedures:

Our main goal is to assess the accuracy and precision of the Dexcom G6 transmitter readings after radiation exposing SOC procedures for which the transmitter is uncovered compared to publicly available accuracy data. Transmitter function will be assessed by comparing the device readings to glucometer readings.

Patients undergoing a TPIAT and planned to receive a Dexcom G6 CGM will be approached for participation in this study prior to post surgery CGM placement.

An anticipated 40 participants will be enrolled and will NOT have a lead apron used to cover their Dexcom G6 device during radiation exposure procedures performed while participant is inpatient post TPIAT.

Dexcom G6 CGM data and point of care (POC) testing with a glucometer (such as the ACCU-CHEK® Inform II Meter) will be utilized for this study while inpatient and a standard issue meter when outpatient. While participants are inpatient POC monitoring will occur every 1 hour when insulin administration is administered intravenous and every 3 hours with the transition to subcutaneous insulin administration. Inpatient POC glucose values and Dexcom reports will be collected. Once discharged, CGM and glucometer readings will be collected by downloading readings using software at the 1 (+/-3 days) week post discharge clinic visit, 1 month (+/- 7 days) post TPIAT, 2 months (+/- 7 days) post TPIAT and before the transmitter is due to be changed (expected 3 months (+/- 7 days) post TPIAT).

The Dexcom CGM has an online platform called Clarity that can generate reports or raw data files of continuous glucose readings. The home glucometer used for the study has a mobile app that can generate reports or raw data files of glucometer readings. Reports will be reviewed at the time of set data download time points by delegated study staff.

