Downloaded data will be stored on a secure server utilizing the participants study ID.

Participants will be requested to check their glucose values with the Contour glucometer 4 times a day for the ten days leading up to study data requests at study time points, but we will accept a minimum of 2 times per day the 7 days prior to a scheduled download to compare the functionality of the Dexcom G6 CGM. Participants (or parents) will be contacted and reminded to check blood sugars at the beginning of this 10-day period at each time point.

While participant is inpatient post TPIAT and outpatient for the life of the CGM transmitter, the number of and type of radiation procedure will be collected from their EMR.

After discharge participants will be contacted at the 1 (+/-3 days) week post discharge clinic visit, 1 month (+/- 7 days) post TPIAT, 2 months (+/- 7 days) post TPIAT and before the transmitter is due to be changed (expected 3 months post TPIAT). Participants will be asked to provide information on any radiation procedures that may have occurred outside of CCHMC, and study staff will confirm the transmitter has not yet been changed. If at any point the transmitter is changed for any reason, the participant will no longer be actively enrolled in the study but data for the transmitter will be collected. If the transmitter is changed due to clinical recommendations such as due to technical issues with readings or calibrations or due to radiologic procedures in which it is in the field of interest, they will be considered completed in the study. If the transmitter is changed due to participant preference with no reason to believe the transmitter was not working properly or needed to be removed for clinical procedures then the participant will be withdrawn. Any termination of participation prior to the anticipated approximately 3-month post TPIAT time point will be noted with reason for early completion/withdraw recorded.

Formal statistical analysis will assess accuracy of the Dexcom transmitter between the publicly available accuracy data and the enrolled participant data. Performance evaluation will include the proportion of CGM values within +/-20% of the reference (POC) glucose values > 100 mg/dL or within +/-20 mg/dL of reference glucose values < 100 mg/dL (%20/20, the analogous %15/15, and the mean absolute relative difference (MARD, expressed as a percentage)

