CONTROL GROUP: Publicly available accuracy data from Dexcom

EXPOSURE GROUP: patients who will NOT have the CGM covered during radiologic procedures involving x-rays.

Standard of care at CCHMC is that sensor values do not replace point of care (POC) testing with a glucometer (such as the ACCU-CHEK® Inform II Meter) while inpatient. POC monitoring will occur every 1 hour when insulin administration is administered intravenous and every 3 hours with the transition to subcutaneous insulin administration. After discharge a provider and family may choose to space out these glucometer readings and eventually transition to relying only on CGM values for SOC, but for this study we are asking families to conduct regular glucometer checks to have comparison data at our study time points.

The following data will be collected during the life of the transmitter (approximately 3 months after placement):

- POC glucose values (from inpatient and outpatient glucometers)
- Dexcom CGM Clarity reports (inpatient and outpatient)
- Timing of interfering substances (hydroxyurea)
- Dates of clinically indicated x-rays and CT scans and radiation exposures (RADS) to radiation field of interest
- Indication for radiologic testing (nausea, vomiting, fever, pain, etc)
- Documentation of apron use during radiologic assessment

The G6 transmitter will be issued while inpatient and be sent home with the families at discharge. Assessment of Dexcom reports compared to POC and home monitoring will be collected at 1 (+/-3 days) week post discharge clinic visit, 1 month (+/- 7 days) post TPIAT, 2 months (+/- 7 days) post TPIAT and before the transmitter is due to be changed (expected 3 months post TPIAT).

Two endocrine providers will perform the clinical assessment of the outpatient reports of glucometer and CGM. Formal analysis will be completed after 3 months of transmitter data is collected.

Statistical Consideration

Several accuracy methods will be ascertained. The %20/20 and%15/15 will be assessed from the participant's medical record for both inpatient and outpatient settings will be reviewed. In addition, use of Clark Error Grid Analysis will be performed on data points collected after 10 hours of hydroxyurea dosing.

Recruitment

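### Month-2 and month-3 accuracy describes only transmitters still in use: one changed for reading problems at home may add few matched pairs while failing, and none afterwards

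*Combined protocol and SAP*

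**What the plan says.** - **End of accuracy follow-up.** Study Intervention: "Transmitter accuracy and precision will be monitored for 3 months post TPIAT or until the transmitter is changed".
- **Status after a change.** Study Procedures says that after any change "the participant will no longer be actively enrolled in the study but data for the transmitter will be collected". It then takes the case "If the transmitter is changed due to clinical recommendations such as due to technical issues with readings or calibrations", joins to it removals because the device lies in the imaging field, and says of both groups that "they will be considered completed in the study". A change by preference alone is a withdrawal. The reason for ending early is recorded.
- **Home reference checks.** Study Procedures asks for checks "4 times a day for the ten days leading up to study data requests at study time points". The same sentence then sets a lower floor for what counts as enough: "we will accept a minimum of 2 times per day the 7 days prior to a scheduled download". Analysis and Methods says that after discharge the provider and family may space out meter readings and "eventually transition to relying only on CGM values for SOC".
- **Other meter data.** Analysis and Methods lists inpatient and outpatient glucometer values over the life of the transmitter, without limiting them to the requested periods. In hospital, checks are hourly on intravenous insulin and 3-hourly on subcutaneous insulin.
- **Review.** Study Procedures: "Reports will be reviewed at the time of set data download time points by delegated study staff". No download is tied to a change.
- **Measures.** %20/20, %15/15 and MARD use CGM and reference values matched in time, and Statistical Consideration adds an error grid. Time to transmitter replacement is a separate item under Study End Points, compared with standard device life.

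**The concern.** The study exists to find out whether a transmitter exposed to radiation loses accuracy later in its roughly 3-month life; the Background faults earlier work for not following it that long. A transmitter that goes wrong at home is likely to be noticed and changed. From then on it supplies no matched pairs. If the bad spell fell between check periods, it may have supplied few before then. A bad CGM value without a reference reading cannot count against the device in any of the accuracy measures.

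Late accuracy is thus conditional on the transmitter having been judged good enough to keep. The plan gives no rule for bringing failed transmitters into the accuracy result, and the completed status puts them in one group with devices removed for imaging. A favourable month-3 figure could be read as showing no delayed damage when it shows only that the remaining transmitters work.

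**Working it through.** **The plan's own figures.** The documents give no failure rate, lag to replacement, discharge day or expected late accuracy, so there is no figure to reproduce. The sample size of 40 has no derivation and is not in dispute here.

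**Inputs from the protocol.** Data requests fall 1 week after discharge and at 1, 2 and 3 months after surgery, taken as days 30, 60 and 90. Requested: 4 checks a day for 10 days before each. Accepted minimum: 2 a day for 7 days.

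**Assumptions, not in the documents.** Discharge on day 14 or 21; onset of failure equally likely on each outpatient day that lets the change occur by day 90; lag L from onset to change of 1 to 7 days; no home checks outside the requested periods; visits exactly on schedule.

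**Step 1: days covered.** Let D = 90 − discharge day. On the full schedule, the periods before days 60 and 90 leave two 20-day gaps (days 30–49 and 60–79). At the minimum the gaps are 23 days each (30–52 and 60–82), plus a 2-day gap (21–22) if discharge is on day 14.

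**Step 2: share of home failures adding no requested pairs.** A failure adds none if all L days lie in one gap of length g:

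share = Σ max(g − L + 1, 0) / (D − L + 1)

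| Schedule | Discharge | Days covered | L = 1 | L = 7 |
|---|---|---|---|---|
| Full | day 14 | 36/76 = 47% | 40/76 = 53% | 28/70 = 40% |
| Full | day 21 | 29/69 = 42% | 40/69 = 58% | 28/63 = 44% |
| Minimum | day 14 | 28/76 = 37% | 48/76 = 63% | 34/70 = 49% |
| Minimum | day 21 | 23/69 = 33% | 46/69 = 67% | 34/63 = 54% |

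The range is 40% to 58% on the full schedule and 49% to 67% at the minimum.

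**Step 3: pairs per transmitter.** Averaged over onset days, a home failure adds about 1.7 to 12 requested bad pairs on the full schedule, or 0.7 to 4.4 at the minimum. A surviving transmitter adds 29 × 4 = 116 to 36 × 4 = 144, or 23 × 2 = 46 to 28 × 2 = 56.

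**Step 4: direction only, purely hypothetical.** Suppose 4 of 40 transmitters fail at home, discharge is on day 21, L = 3, and 93% of good and 50% of bad pairs meet 20/20. In the month-3 period (40 checks per transmitter) the 36 others give 36 × 40 = 1,440 pairs. Averaged over the 67 possible onset days, the 4 failing ones give 28/67 × 4 × 4 = 6.7 good and 27/67 × 4 × 4 = 6.4 bad pairs.

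- Reported: 93 − 43 × 6.4/1,453 = 92.8%.
- With the failed transmitters still represented: (36 × 93 + 4 × 50)/40 = 88.7%.
- With 8 failures: 93 − 43 × 12.9/1,306 = 92.6%, against (32 × 93 + 8 × 50)/40 = 84.4%.

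The reported figure hardly moves while the contrast does. The failure rates and the 93% and 50% are invented, so the gap is not an estimate for this trial.

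**The case against.** The strongest reply is that the plan loses less than it seems to. Data for a changed transmitter are kept, outpatient meter values are collected throughout its life, and the reason for ending early is recorded. Families only may choose to rely on CGM. Risk Assessment has them checking every 3 to 4 hours in the immediate post-operative period, and the Background describes comparing sensor with meter over the 3 months after surgery. A change for reading problems may itself have followed a meter comparison. Replacement is a stated endpoint. The completed status deletes nothing, and a removed transmitter can give no later pairs under any label. Finally, the public comparator data may also describe only working devices.

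Most of this stands, and it rules out several stronger readings:

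- A reader might infer that failed transmitters drop out of the accuracy data. They do not: pairs up to the change are retained.
- A reader might infer that no meter readings exist between check periods. The text permits that but does not state it.
- A reader might take the share of outpatient days without requested checks (53% to 58% on the full schedule) as the share of failures unseen. A failure that starts in a gap and lasts into a check period adds pairs.
- A reader might extend the shortage of pairs to hospital failures. Checks every 1 to 3 hours, or 8 to 24 a day before hydroxyurea exclusions, would record those.
- A reader might treat a shift of several percentage points in %20/20 as shown. No input for it is in the documents.

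One part does not answer the point. Keeping data does not create reference readings that were never requested, and the replacement endpoint is set against device life, not joined to accuracy. The comparator argument limits how a corrected figure may be used; it does not make the late figure describe all exposed transmitters.

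**Conclusion.** The concern holds for failures at home, mainly after the early post-operative period. Month-2 and month-3 %20/20, %15/15, MARD and error grid results describe the transmitters still in use, and they lean toward no effect on the study's central question. The direction follows from the follow-up and matching rules, provided that transmitters changed for reading problems are less accurate than those kept.

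The size is unknown. The 40% to 58% (49% to 67% at the minimum) rests on the assumed discharge days, the 1 to 7 day lag, uniform onset and no off-period checks. Any such checks would lower it, and the ±7-day visit windows would move the periods. The point deserves action before data are collected, because missing reference readings and unrecorded categories are hard to recover later.

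**What to change.** 1. Record three separate outcomes: changed for a reading or calibration problem, removed because of the imaging field, and reached 3 months.
2. At each time point, report accuracy together with the number of original transmitters still in use and the cumulative number changed for reading problems.
3. Add a sensitivity result that counts transmitters changed for reading problems as not meeting the accuracy limit from the change onward. It suits %20/20 and %15/15; MARD would need an imputed value. Label it as not directly comparable with the public accuracy data, whose handling of failed devices is not known from the documents.
4. Without delaying any change, download the available CGM and meter data at the change and analyse them as that transmitter's final time point. This may yield few pairs, so items 2 and 3 matter most.

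The cost is protocol wording, one remote download per failure and one extra table. The small downside is that late accuracy may look slightly less favourable.

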Primary Objective	To determine if standard of care radiation exposure longitudinally effects the accuracy and precision of the G6 transmitter in the post TPIAT inpatient population
Secondary Objective(s)	Reduce burden for patients to remove and waste a functional and expensive Dexcom G6 CGM for radiologic procedures.
Research Intervention	Participants will have their study provided Dexcom G6 CGM uncovered for standard of care procedures that involve radiation exposure while inpatient at CCHMC
IND/IDE #	NA
Study Population	Post total pancreatectomy with islet autotransplantation (TPIAT) patients
Sample Size	N = 40
Study Duration for individual participants	3 months of active study participation

Abbreviations	total pancreatectomy with islet autotransplantation (TPIAT) Identification, ID Principal Investigator, PI Good Clinical Practice, GCP Adverse Reactions, AE Severe Adverse Reactions, SAEs continuous glucose monitoring (CGM) point of care (POC) Data and Safety Monitoring Board (DSMB) Standard of Care (SOC)
----------------------	--

Study Objective

We will establish accuracy and precision data for the lifespan (up to about 3 months) of the Dexcom G6 transmitter exposed to inpatient radiation (x-ray and/or CT scan) that is not covered with lead apron.

Background

There are limited data published regarding the accuracy and precision of continuous glucose monitoring (CGM) devices after radiation exposure. While manufacturers, specifically Dexcom, recommend to remove CGM systems with MRI and CT scan there is some ambiguity surrounding radiation exposure from a diagnostic x-ray as only a few cross-sectional studies have been conducted [1]. Spanakis et al assessed the accuracy and precision of Dexcom two hours pre- and post-imaging. They reported that ongoing CGM use during multiple radiology procedures was safe and reliable based on 98.1% of glucoses falling into Zone A and B of Clark Error Grid analysis which represents values that result in no difference in clinical decision making. However, this analysis did not assess the transmitter longitudinally to ensure accuracy over its 3-month lifespan. A second report, based on simulation of a radiotherapeutic procedure (80 GY) found that the components of G6 retained basic functionality and data integrity after exposure and again did not include assessment of the transmitters 3-month lifespan.

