At CCHMC, we are in the unique position to work with a hospitalized population who utilize Dexcom G6 CGMs while inpatient. The patients are children and adolescents who have had a total pancreatectomy with islet autotransplantation (TPIAT) and receive, on average, 6 radiology procedures (defined as CT scans or x-rays) over a 2-week period following TPIAT. This population has a target glucose range of 80-120 mg/dL and Dexcom is used to monitor trends under careful oversight by the pediatric endocrinology service. Because these patients represent a complex surgical population, they often have post-operative events that include abdominal pain, vomiting, and fever. Radiology procedures are frequently obtained for

assessment of obstruction, abscesses and/or thrombi. At our institution if the sensor and transmitter is not in the field of interest, current practice is to cover the Dexcom (sensor and transmitter) during all radiology procedures with a lead apron and have careful assessment of sensor values compared to glucometer glucose readings while in-hospital and the 3 months post-operatively. The repeated radiation exposure over a short timeframe (2-3 weeks) in the context of established monitoring of device performance by providers who specialize in pediatric diabetes management makes this population ideal for studying CGM performance. A transmitter is changed every 3 months and a sensor is changed every 7-10 days.

Rationale

It is of great burden for patients to remove and waste functional and expensive medical equipment for radiologic procedures, especially if there are repeated procedures planned over a short period. There is minimal data to suggest, at least in the short term, that accuracy and precision is not affected by radiation in commonly ordered radiology procedures. Our aim is to contribute to this knowledge base and assess *longitudinally* the accuracy and precision of the G6 transmitter during and after exposure to radiation in an inpatient post-TPIAT population.

Study End Points:

CGM readings will be assessed for accuracy and precision. Publicly available accuracy data will be compared to study glucometer readings over the 3 months expected lifespan of the Dexcom G6 CGM transmitter used post TPIAT.

Time to Dexcom G6 CGM transmitter replacement needed over the 3 months post TPIAT will be compared to the standard device life expectancy.

We will take the following into consideration with our analysis:

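### The objective is accuracy and precision over the transmitter's life, but no planned statistic is tied to a time point, separates bias from scatter, or allows for repeated pairs

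*Combined protocol and SAP*

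**What the plan says.** The Study Summary gives the primary objective as: "To determine if standard of care radiation exposure longitudinally effects the accuracy and precision of the G6 transmitter in the post TPIAT inpatient population". The Background faults two earlier studies for not following the transmitter over its 3-month life, and the Rationale stresses the longitudinal aim.

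Study Procedures and Analysis and Methods place the CGM-meter comparison at four outpatient time points: 1 week after discharge, then about 1, 2 and 3 months after TPIAT. For each, families are asked for four checks a day over ten days, although "we will accept a minimum of 2 times per day the 7 days prior to a scheduled download".

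The analysis is described in three places:

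- **Study End Points:** "Publicly available accuracy data will be compared to study glucometer readings over the 3 months expected lifespan of the Dexcom G6 CGM transmitter", and separately "Time to Dexcom G6 CGM transmitter replacement needed over the 3 months post TPIAT will be compared to the standard device life expectancy".
- **Study Procedures:** "Formal statistical analysis will assess accuracy of the Dexcom transmitter between the publicly available accuracy data and the enrolled participant data", using %20/20, %15/15 and MARD.
- **Statistical Consideration:** %20/20 and %15/15 for inpatient and outpatient settings, plus an error grid on data outside the hydroxyurea window.

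The reference meter changes at discharge, from a hospital point-of-care meter to "a standard issue meter when outpatient".

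**The concern.** What this study adds to the earlier short-term work is the course of accuracy and precision over three months. The data are collected at time points, but no metric is assigned to any of them, and no trend or early-late contrast is named. The one stated split cannot stand in for such a contrast, because setting and reference meter change together.

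Precision is in the objective, but every listed number is an unsigned agreement measure or a zone share. No mean signed difference and no SD of differences is named. If accuracy fell, the listed numbers would not say whether the device had shifted, in which direction, or had become noisier.

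Each participant supplies many pairs from one transmitter and several sensors ("A transmitter is changed every 3 months and a sensor is changed every 7-10 days"). The plan does not say how that dependence will be handled if intervals or tests are reported.

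**Working it through.** **Plan's own figure.** There is none to reproduce. The sample size of 40 has no alpha, power, effect size, SD or margin attached. The figures below illustrate consequences. Inputs marked *assumed* are not in the documents. The hydroxyurea exclusion is not applied to counts because dosing frequency is not given.

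**1. Dilution of a late fall.** *Assumed:* %20/20 falls from 92% to 80% (12 points) at month 3 only. Fall shown = month-3 share of pairs × 12.

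From Study Procedures, pairs per window are 2 × 7 = 14 (accepted minimum) or 4 × 10 = 40 (requested).

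- Outpatient only, four equal windows: 1/4 × 12 = 3.0 points.
- 14 pairs at month 3 and 40 in each earlier window: 14/134 = 10.4%, or 1.3 points. The reverse: 40/82 = 48.8%, or 5.9 points.

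If inpatient pairs are pooled too, inpatient pairs = 24 × IV days + 8 × (stay − IV days), from hourly and 3-hourly testing. *Assumed:* stay 14-21 days, IV insulin 2-14 days.

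- Lowest count: 24 × 2 + 8 × 12 = 144. Highest: 24 × 14 + 8 × 7 = 392.
- Month-3 share: from 14/(392 + 134) = 2.7% to 40/(144 + 82) = 17.7%, or 0.3 to 2.1 points.

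**2. Bias or scatter.** *Assumed:* normal relative differences with mean b and SD s, reference above 100 mg/dL. MARD = s√(2/π)·exp(−b²/2s²) + b[1 − 2Φ(−b/s)]. Proportion within 20% = Φ((20 − b)/s) − Φ((−20 − b)/s), and likewise for 15%.

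| Bias | SD | MARD | Within 20% | Within 15% |
|---|---|---|---|---|
| 0 | 11.3% | 9.0% | 92.4% | 81.6% |
| +8% or −8% | 11.3% | 11.2% | 85.0% | 71.2% |
| 0 | 14.0% | 11.2% | 84.7% | 71.6% |

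The last two rows are practically indistinguishable, and the sign of the shift is lost. Levels change below 100 mg/dL, where the band is absolute: at 80 mg/dL it is ±25%, and the starting 92.4% becomes 97.3%. The target range is 80-120 mg/dL, so both regions matter.

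**3. Repeated pairs.** Ratio of clustered to pair-level half-width = √(1 + (m − 1) × ICC). *Assumed:* ICC 0.02 to 0.20.

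- m = 14, ICC 0.02: √1.26 = 1.12.
- m = 40, ICC 0.20: √8.8 = 2.97.

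**4. Is an early-late contrast workable?** Variance = [ICC(v₁ + v₂ − 2r√(v₁v₂)) + (1 − ICC)(v₁ + v₂)/m]/N, with v = p(1 − p). *Assumed:* early p = 0.92, late p = 0.92 or 0.80, ICC 0.02-0.20, between-window correlation r = 0-0.5, m = 14-40 in each window. Half-width = 1.96 × SE.

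- N = 40: 2.2 to 7.6 points. N = 30: 2.6 to 8.8. N = 15: 3.6 to 12.4.
- The 12.4 comes from N = 15, ICC 0.20, r = 0, m = 14 and late p = 0.80: v₁ + v₂ = 0.0736 + 0.16 = 0.2336; (0.20 × 0.2336 + 0.80 × 0.2336/14)/15 = 0.0040; 1.96 × √0.0040 = 12.4 points.
- At ICC 0.10 the same case gives (0.10 × 0.2336 + 0.90 × 0.2336/14)/15 = 0.00256, or 9.9 points.

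These treat both windows as equal in size. A merged early window would hold more readings, with a small effect. N = 15 is the low end of the rate in Study Timelines (1-2 a month for 15-19 months, so 15 to 38). The rate in Available Resources (36-48 a year) gives 45 to 76.

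**The case against.** The strongest reply is that the plan is longitudinal already. Analysis and Methods sets the comparison of CGM with meter readings at the named visits and says home checks are requested so that comparison data exist at those points. Study End Points speaks of the 3-month lifespan, two providers review the outpatient reports, and time to replacement is itself a longitudinal endpoint. The Study Objective is to establish lifespan data, and Study Procedures calls comparison with public data the main goal. A three-month summary against a benchmark is thus a fair reading, and an early-late contrast is one option among several.

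Much of this stands. The data allow time-specific estimates, and the benchmark comparison should stay. But the visit text fixes collection without naming a statistic, the provider review is a clinical assessment set apart from the formal analysis, and replacement measures device survival. A transmitter can drift without being replaced.

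On precision, the Background reports an earlier study's accuracy and precision as "98.1% of glucoses falling into Zone A and B of Clark Error Grid analysis", and the same grid is planned. The grid's plot shows direction informally, but a zone share mixes shift with scatter.

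Two further points stand. No interval or test is specified, so the harm from ignoring clustering is conditional. And with no concurrent unexposed group, a late fall could reflect ordinary ageing of the device or changing patient state. A contrast over time would not by itself show a radiation effect.

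**Conclusion.** The gap is real and should be closed before analysis. The named statistics can describe overall accuracy against public data, including a shift that is present early and persists. They do not estimate change over transmitter life, and they do not separate bias from scatter.

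The sizes are illustrative and rest on the assumed fall, normal errors, ICC and length of stay. A 12-point fall at month 3 shows as 3.0 points with equal outpatient windows (1.3 to 5.9 with uneven completion). The 0.3 to 2.1 points apply only if inpatient pairs are pooled as well. The setting split is stated for %20/20 and %15/15 but not for MARD.

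Three stronger readings are not supported:

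- A reader might infer that all pairs will be pooled and treated as independent. The documents do not say so; they are silent.
- A reader might infer that the study cannot answer its longitudinal question. The readings needed to describe change over time are already scheduled.
- A reader might infer that the listed metrics would miss a shift. They worsen under one, but do not identify it.

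**What to change.** 1. Keep the comparison with public data. Report %20/20, %15/15, MARD, mean signed relative difference, and both total and within-participant SD of the relative difference, separately for inpatient, 1 week, 1, 2 and 3 months. Count each reading once where look-back periods overlap. The within-participant SD is needed because the total SD also contains differences between participants.
2. Pre-specify one early-late contrast among outpatient readings only, so that the hospital-to-home meter change does not enter it. Early is the merged post-discharge readings from the 1-week and 1-month look-backs. Late is the 3-month window, in participants whose original transmitter is still in use. As a sensitivity analysis for transmitters changed earlier, use the last available outpatient window after the early one, and report the number and reasons for those with none.
3. Give estimates with participant-clustered intervals, from a participant bootstrap or a mixed model.
4. State that the contrast describes change over transmitter life, cannot alone attribute that change to radiation, and cannot show a shift already present in the early window. Read it alongside time to replacement.

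The cost is analysis wording and a few more tables, with no new visits or checks. Intervals will be wider than pair-level ones, and single-window estimates will be less precise than pooled ones. With about 15 participants at month 3, the half-width exceeds 12 points only under the least favourable assumptions (about ICC 0.20, no between-window correlation, 14 pairs per window).
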